6.1.2 Treatment arms/group

This is an open-label study where all subjects will receive one injection of brolucizumab 6 mg PFS at Baseline.

6.1.3 Treatment duration

One injection of brolucizumab 6 mg PFS per subject will be administered at Baseline, with one End of Study follow up visit after 7 days (\pm 2 days).

6.2 Other treatment(s)

6.2.1 Concomitant therapy

All medications, procedures and significant non-drug therapies administered after the subject was enrolled into the study must be recorded on the appropriate electronic Case Report Forms (eCRF). As needed, treatment of the fellow eye will be performed according to clinical practice and the used medication or procedure should be reported in the eCRF.

6.2.2 Prohibited medication

Use of the treatments displayed in the below table is NOT allowed at the start of the investigational drug.

Table 6-2 Prohibited medication

Medication	Prohibition period	Action taken
Anti-VEGF therapy other than IP in study eye	At Baseline	Discontinue study
Intraocular or periocular injections of corticosteroids (except if treatment for AE) in study eye	At Baseline	Discontinue study

6.3 Subject numbering, treatment assignment, randomization**6.3.1 Subject numbering**

Each subject is identified in the study by a Subject Number (Subject No.) that is assigned when the subject is first enrolled for screening and is retained as the primary identifier for the subject throughout his/her entire participation in the trial. The Subject No. consists of the Center Number (Center No.) (as assigned by Novartis to the investigative site) with a sequential subject number suffixed to it, so that each subject is numbered uniquely across the entire database. Upon signing the informed consent form, the subject is assigned to the next sequential Subject No. available.

6.3.2 Treatment assignment, randomization

Treatment assignment and randomization is not applicable for this open-label study.

6.4 Treatment masking

This is an open-label study, therefore treatment will be open to subjects, investigator staff, and observational study participants including qualified ophthalmologists and their assistants and representatives of the sponsor.

6.5 Dose escalation and dose modification

Dose escalation and modification is not permitted in this study.

6.6 Additional treatment guidance**6.6.1 Treatment compliance**

The subject will receive only one intravitreal injection of broloclizumab 6 mg PFS performed by a qualified ophthalmologist. For this injection the appropriate eCRF will be completed.

6.6.2 Emergency breaking of assigned treatment code

Emergency breaking of assigned treatment code is not applicable, since this is an open label study, where each subject receives one injection of broloclizumab 6 mg via PFS.

6.7 Preparation and dispensation

Each study site will be supplied with study drug in packaging as described under investigational and control drugs [Section 6.1.1](#).

A unique medication number is printed on the study medication label.

The study medication has a 2-part label (base plus tear-off label). Immediately before the IVT is performed, site personnel will detach the outer part of the label from the package and affix it to the subject's source document.

6.7.1 Handling of study treatment and additional treatment

6.7.1.1 Handling of study treatment

Study treatment must be received by a designated person at the study site, handled and stored safely and properly and kept in a secured location to which only the investigator and designated site personnel have access. Upon receipt, all study treatment must be stored according to the instructions specified on the labels and in the Investigator's Brochure (IB). Clinical supplies are to be dispensed only in accordance with the protocol. Technical complaints are to be reported to the respective Novartis Country Organization Quality Assurance.

Medication labels will be in the local language and comply with the legal requirements of each country. They will include storage conditions for the study treatment but no information about the subject except for the medication number.

The investigator must maintain an accurate record of the shipment and dispensing of study treatment in a drug accountability log. Monitoring of drug accountability will be performed by monitors during site visits or remotely and at the completion of the trial. Subjects will be asked to return all unused study treatment and packaging at the end of the study or at the time of discontinuation of study treatment.

At the conclusion of the study, and as appropriate during the course of the study, the investigator will return all unused study treatment, packaging, drug labels, and a copy of the completed drug accountability log to the Novartis monitor or to the Novartis address provided in the investigator folder at each site.

6.7.2 Instruction for prescribing and taking study treatment

The IVT injection will be carried out under controlled, aseptic conditions per local clinical practice. The study eye will be assessed before and after intravitreal injection to ensure that the procedure and/or the study treatment had not endangered the health of the eye. An IVT injection is contraindicated in subjects with active ocular-or periocular infections and in subjects with active intraocular inflammation; therefore, the investigator should verify that these conditions are not present in either eye (study and fellow eyes) prior to the injection.

All kits of study treatment will be recorded/databased. Date and time of every injection administered to the subject will be recorded in the eCRF.

Additionally, the conduct of IVT injections brolucizumab 6 mg PFS will be observed by an external team under observational protocol [REDACTED].

[REDACTED]

7 Informed consent procedures

Eligible subjects may only be included in the study after providing (witnessed, where required by law or regulation), IRB/IEC-approved informed consent.

If applicable, in cases where the subject's representative(s) gives consent (if allowed according to local requirements), the subject must be informed about the study to the extent possible given his/her understanding. If the subject is capable of doing so, he/she must indicate agreement by personally signing and dating the written informed consent document.

Informed consent must be obtained before conducting any study-specific procedures (eg all of the procedures described in the protocol). The subject will also need to consent that the injection procedure and observation is video recorded. The process of obtaining informed consent must be documented in the subject source documents.

Novartis will provide to investigators in a separate document a proposed informed consent form that complies with ICH/GCP guidelines and regulatory requirements and is considered appropriate for this study. Any changes to the proposed consent form suggested by the investigator must be agreed by Novartis before submission to the IRB/IEC.

Information about common side effects already known about the investigational drug can be found in the Investigator's Brochure (IB). This information will be included in the subject informed consent and should be discussed with the subject during the study as needed. Any new information regarding the safety profile of the investigational drug that is identified between IB updates will be communicated as appropriate, for example, via an investigator notification (IN) or an aggregate safety finding. New information might require an update to the informed consent and then must be discussed with the subject.

Women of child bearing potential must be informed that taking the study treatment may involve unknown risks to the fetus if pregnancy were to occur during the study and agree that in order to participate in the study they must adhere to the contraception requirements.

A copy of the approved version of all consent forms must be provided to Novartis after IRB/IEC approval.

8 Visit schedule and assessments

The Assessment Schedule ([Table 8-1](#)) lists all of the assessments when they are performed. All data obtained from these assessments must be supported in the subject's source document.

Subjects should be seen for all visits/assessments as outlined in the Assessment Schedule ([Table 8-1](#)) or as close to the designated day/time as possible. Missed or rescheduled visits should not lead to automatic discontinuation. Subjects who prematurely discontinue the study for any reason should be scheduled for a visit as soon as possible, at which time all of the assessment of the final visit will be performed. At this final visit, the adverse event and concomitant medications should be recorded on the eCRF.

Table 8-1 Assessment Schedule

Period	Open Label Treatment	Post-Treatment Follow-Up	Follow up
Visit Name	Baseline	End of Study	Follow up
Days	1	8	31
Informed consent	X		
Inclusion / Exclusion criteria	X		
Demography	X		
Medical history/current medical conditions	X		
Concomitant medications	X	X	
Intraocular Pressure (IOP)	X	X	
Vital Signs	X	X	
Pregnancy Test	S		
Study drug administration	X		
Observation of PFS injection	S		
Adverse Events	X	X	S
Ocular Assessments (slitlamp, ophthalmoscopy)	S	S	

^X Assessment to be recorded in the clinical database or received electronically from a vendor

^S Assessment to be recorded in the source documentation only

8.1 Screening

Subjects who sign an informed consent form, meet all of the inclusion and exclusion criteria, will receive one injection of Brolucizumab 6 mg PFS in the study eye at Baseline.

The conduct of the IVT injection and preparation will be observed and videotaped by 2 observers and will follow observational study protocol [REDACTED], which aims to assess the ability of observational study participants, including qualified ophthalmologists and assistants who may perform the preparation steps, to prepare and administer to subjects an IVT injection using brolucizumab 6 mg PFS and to follow the IFU.

Re-screening is not allowed in this protocol.

8.1.1 Information to be collected on screening failures

There is no separate screening period planned for this study. Subject's Eligibility will be assessed at the Baseline Visit.

Subjects who sign an informed consent but do not receive the IVT injection will be considered a screen failure. The demographic information, informed consent, and Inclusion/Exclusion data must be completed in the eCRF and also be kept in the source documents for screen failure subjects. No further data will be entered into the clinical database for subjects who are screen failures, except if subject experienced a serious adverse event (see SAE section for reporting details).

8.2 Subject demographics/other baseline characteristics

The following data will be documented in the source document: age, sex, race, ethnicity, vital signs, study eye, IOP, date of nAMD diagnosis, concomitant medications, medical history, and current medical conditions.

8.3 Efficacy

Efficacy is not measured in this study. The usability assessments of PFS conducted within this study are specified in observational study protocol [REDACTED]

8.4 Safety

Safety evaluation will include ocular and non-ocular assessments (eg vital signs, IOP, slitlamp and ophthalmoscopy) and will be performed according to the clinical practice. Any clinically significant changes should be reported as AEs.

For details on AE collection and reporting, refer to [Section 10.1.1](#).

The End of Study visit after 7 days (\pm 2) will be done at the site. The ocular assessments like slitlamp and ophthalmoscopy will be recorded in the source document and IOP will be entered in the eCRF. The non-ocular assessment (vital signs) will be recorded in the eCRF.

Additionally, a follow-up phone call 30 days after the End of Study Visit will be performed for subjects with any ongoing AEs at the End of Study Visit. Any occurred adverse events in this period should be collected in the source, and SAEs must be reported to Novartis safety according instructions in [Section 10.1.3](#).

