4.2 Rationale for dose/regimen and duration of treatment

Each subject who enters the study will be given one injection of brolucizumab 6 mg in PFS. Previously performed studies in this indication suggest that brolucizumab 6 mg dose is effective and safe. One injection will be given in order to support the observation of the successful use of the device (PFS). After this injection, the follow up visit at Day 8 will be performed and there will be a safety follow-up phone call at Day 31. Subjects will be considered to have completed the study after the evaluations at Visit 2. The investigator will recommend the appropriate follow-up medical care, as needed and according to the clinical practice, for all subjects who completed the study.

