10.1 Definition of adverse events and reporting requirements

10.1.1 Adverse events

An adverse event (AE) is any untoward medical occurrence (eg, any unfavorable and unintended sign (including abnormal laboratory findings), symptom or disease) in a subject or clinical investigation subject after providing written informed consent for participation in the study. Therefore, an AE may or may not be temporally or causally associated with the use of a medicinal (investigational) product.

The investigator has the responsibility for managing the safety of individual subject and identifying adverse events.

Novartis qualified medical personnel will be readily available to advise on trial related medical questions or problems.

The occurrence of adverse events must be sought by non-directive questioning of the subject at each visit during the study. Adverse events also may be detected when they are volunteered by the subject during or between visits or through physical examination findings, laboratory test findings, or other assessments.

Adverse events must be recorded in the Adverse Events CRF under the signs, symptoms or diagnosis associated with them, accompanied by the following information (as far as possible) (if the event is serious refer to [Section 10.1.2](#)):

1. The severity grade includes the following:
 - mild: usually transient in nature and generally not interfering with normal activities
 - moderate: sufficiently discomforting to interfere with normal activities
 - severe: prevents normal activities
2. its relationship to the study treatment. If the event is due to lack of efficacy or progression of underlying illness (ie progression of the study indication) the assessment of causality will usually be 'Not suspected'. The rationale for this guidance is that the symptoms of a lack of efficacy or progression of underlying illness are not caused by the trial drug, they happen in spite of its administration and/or both lack of efficacy and progression of underlying disease can only be evaluated meaningfully by an analysis of cohorts, not on a single subject.
3. its duration (start and end dates) or if the event is ongoing, an outcome of not recovered/not resolved must be reported.
4. whether it constitutes a SAE (see [Section 10.1.2](#) for definition of SAE) and which seriousness criteria have been met.
5. action taken regarding with study treatment.

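### Protocol 8.4 conflicts with 4.2 and Table 8-1 on the day of the safety call and on who receives it

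*Protocol*

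**What the plan says.** Three places in the current protocol describe contact after the End of Study Visit (Visit 2).

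- **Section 4.2** describes the course of each injected subject: after the Day 8 visit, "there will be a safety follow-up phone call at Day 31". No subset is named. The same section adds that "Subjects will be considered to have completed the study after the evaluations at Visit 2".
- **Table 8-1** has one column after Visit 2, headed Follow up, at Day 31. Adverse events are the only assessment marked there, with the code S, defined as "Assessment to be recorded in the source documentation only". No footnote limits it to some subjects. Section 8 introduces the table as the full list of assessments and instructs sites: "Subjects should be seen for all visits/assessments as outlined in the Assessment Schedule".
- **Section 8.4** says: "Additionally, a follow-up phone call 30 days after the End of Study Visit will be performed for subjects with any ongoing AEs" at that visit. It continues: "Any occurred adverse events in this period should be collected in the source, and SAEs must be reported to Novartis safety". It does not mention Day 31.

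Three other provisions bear on the point. Section 6.1.3 gives one injection "with one End of Study follow up visit after 7 days" (± 2), so there is no later clinic visit. Section 10.1.1 requires AE monitoring for at least 30 days after the injection. Section 10.1.3 requires every SAE from consent to 30 days after the last administration to be reported, within 24 hours of the site learning of it. Neither requirement depends on AE status at Visit 2.

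**The concern.** Section 8.4 is the dedicated safety section and gives the most detailed instructions for the call: who is called, when, where events are recorded and how SAEs are passed on. A site could reasonably treat it as the operative rule. It would then call only subjects whose AE was still ongoing at Visit 2, and would call them after the 30-day period had ended. Subjects with nothing ongoing at Visit 2 would not be called, yet they are the ones in whom any later event would be new.

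At stake is safety follow-up in a study whose only objective is safety. Section 10.1.1 has AEs sought by questioning at each visit, and the last visit is at about Day 8. Without the Day 31 contact, a new event in the rest of the 30-day period comes to light only if the subject volunteers it or it surfaces by another unscheduled route. Different sites could also apply different rules, so follow-up would not be uniform.

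**Working it through.** **Inputs**

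- Injection date = Day 1 (SAP 2.1.1.1).
- End of Study Visit at 7 ± 2 days after Baseline (Protocol 3, 6.1.3, 8.4): Day 8, range 6 to 10.
- Monitoring and SAE reporting period: 30 days after injection (Protocol 10.1.1, 10.1.3).
- About 30 treated subjects at about 3 sites (Protocol 5).
- k = number of subjects with an AE ongoing at Visit 2. The documents do not give it, so the full range 0 to 30 is used.

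**Step 1: reproduce the plan's own day.** Injection + 30 days = 1 + 30 = Day 31. This matches 4.2, Table 8-1 and the 30-day periods in 10.1.1 and 10.1.3.

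**Step 2: date the 8.4 call.** Visit 2 day + 30:

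| Visit 2 | 8.4 call | Days after Day 31 | Days from Visit 2 to Day 31 |
|---|---|---|---|
| Day 6 | 6 + 30 = Day 36 | 36 − 31 = 5 | 31 − 6 = 25 |
| Day 8 | 8 + 30 = Day 38 | 38 − 31 = 7 | 31 − 8 = 23 |
| Day 10 | 10 + 30 = Day 40 | 40 − 31 = 9 | 31 − 10 = 21 |

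The 8.4 call therefore falls 5 to 9 days after the period closes. A subject who is not called has no scheduled enquiry for its last 21 to 25 days.

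**Step 3: count scheduled enquiries after Visit 2, with N = 30.**

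| Reading | Day 31 | Day 38 (36 to 40) | Subjects with none |
|---|---|---|---|
| 4.2 and Table 8-1 | 30 | 0 | 0 |
| 8.4 as the only rule | 0 | k | 30 − k |
| 8.4 in addition to Day 31 | 30 | k | 0 |

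Enquiries lost under 8.4 alone, 30 − k: 30 if k = 0; 27 if k = 3; 20 if k = 10; 0 if k = 30.

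**Step 4: only some sites follow 8.4.** Assume three equal sites, 30/3 = 10 subjects each. The upper bound (k = 0) is 10, 20 or 30 subjects without the enquiry if one, two or three sites do so.

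**Step 5: effect on the analysis.** SAP 2.8.1 summarises AEs from the injection date until the subject completes or discontinues. Completion is at Visit 2 (Protocol 4.2), and AEs at the follow-up contact go into source only (Table 8-1). The planned AE tables are the same under every reading.

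**The case against.** The strongest reply is that the protocol already contains the right rule. Section 8 sends sites to Table 8-1, which has an unrestricted Day 31 AE entry. Section 4.2 repeats the Day 31 call, and 8.4 itself refers AE collection to 10.1.1, which sets the 30-day period. On this view only a site that ignored several other passages would omit the call.

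Section 8.4 also opens with *Additionally* and never says that only these subjects are called. It can be read as an extra call for unresolved events, in line with the duty in 10.1.1 to follow a detected AE to resolution or permanence. On that reading nothing is lost.

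Finally, the duties survive any reading. In-window SAEs remain reportable whenever the site learns of them, and "Adverse events also may be detected when they are volunteered by the subject during or between visits". Subjects with an ongoing AE are being followed anyway, so for them a later call means at most delay. The 30 − k count depends on an assumed misreading whose likelihood the documents do not show.

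Most of this stands, and it limits the consequence. It does not remove the conflict. If the 8.4 call is extra, it is missing from a table presented as listing every assessment, and 8.4 does not mention the call it is supposed to supplement. If it is not extra, it contradicts the table on both day and population. The text needs correcting either way. A surviving duty to report also does not replace a scheduled enquiry, because a site can report only what it learns.

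**Conclusion.** The concern holds. Section 8.4 conflicts with 4.2 and Table 8-1 on timing (Day 38, range 36 to 40, against Day 31) and on population (subjects with an ongoing AE against no restriction), and no text reconciles them.

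The text conflict is certain; its practical consequence is conditional. If 8.4 is taken as the only rule, 30 − k of about 30 subjects lose their one scheduled end-of-period enquiry, and the k who are called are asked 7 (5 to 9) days late. If sites follow Table 8-1, or treat 8.4 as an additional call, no enquiry is lost. The counts rest on N = 30, an unknown k and, for the site bounds, three equal sites. The documents do not allow an estimate of SAEs missed or delayed. The planned AE tables do not change.

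This should be fixed. It is an operative safety instruction in a study with safety as its sole objective, although it does not threaten the planned analysis.

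**What to change.** Amend 8.4 to schedule a safety follow-up call at Day 31, 30 days after injection, for every treated subject, with any AE still ongoing at that call followed further under 10.1.1. This brings 8.4 into line with 4.2, Table 8-1, 10.1.1 and 10.1.3.

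If a later call for subjects with ongoing AEs is also wanted, state in 8.4 that it is additional to the Day 31 call and add a column for it to Table 8-1.

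The cost is one sentence in 8.4, plus one table column if the later call is kept. The main change adds no calls beyond the roughly 30 that 4.2 and Table 8-1 already schedule. The SAP needs no change.

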8.4.1 Pregnancy and assessments of fertility

A urine pregnancy test will be conducted for all women of childbearing potential to assess pregnancy before inclusion in the study.

Additional pregnancy testing may be performed if requested by local requirements.

9 Study discontinuation and completion

9.1 Discontinuation

9.1.1 Discontinuation of study treatment

This is a single dose study, therefore discontinuation of study treatment is not applicable.

Subjects who decide they do not wish to participate in the study further should NOT be considered withdrawn from the study UNLESS they withdraw their consent (see withdraw of informed consent [Section 9.1.2](#)). **Where possible, they should return for the assessments indicated** in the assessment schedule. If they fail to return for these assessments for unknown reasons, every effort (eg telephone, e-mail, and letter) should be made to contact the subject/pre-designated contact as specified in the lost to follow-up section. This contact should preferably be done according to the study visit schedule.

If the subject cannot or is unwilling to attend the follow up visit at Day 8, the site staff should maintain regular telephone contact with the subject, or with a person pre-designated by the subject. This telephone contact should preferably be done according to the study visit schedule.

